A data collection form (Appendix 1) will be used to collect information about the subject. This information will be obtained by the research fellow during his private interview with the patient after consent is taken. Some data will also be obtained from the electronic health records by the same CITI certified research fellow. Data will be related to AF and to the risk stratification tool (AFCVS score). Variables include demographics (age, gender), metrics (BMI, waist-hip ratio), past medical history (hypertension, diabetes mellitus, etc.), past surgical history (CABG, PCI, etc.), medications, social history, vital signs, physical exam, echocardiography results, NYHA score.

i) Sample size

There are no similar studies published in the literature assessing the efficacy of DSED on refractory AF. Accordingly, for the purpose of sample size calculation, the investigators considered a conservative approach in the calculation. More specifically, the investigators considered that 50% of patients with refractory AF will revert to sinus rhythm after 3 trials of DC cardioversion. Based on clinical experience, the investigators expect 78% to achieve

positive outcome after 2 trials of DC cardioversion followed by a third trial of DSED. This will yield an expected difference of 28% in DSED between the intervention and control groups. Considering a power of 80% and an alpha of 0.05, the investigators will require 50 patients in each arm, a total of 100 patients.

j) Statistical analysis

In the univariate analysis, the distribution will be presented as means \pm standard deviations and frequencies (percentage) for the continuous and categorical variables, respectively. In the bivariate analysis, student's t-test and Pearson's chi-square test will be used to assess the significance of the statistical association between the independent variables (continuous and categorical) and the two groups (Intervention and control) of the outcome. Furthermore, results will be presented as odds ratios (OR) and their corresponding 95% confidence intervals (CI).

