A multivariate analysis will be carried out for the association between the intervention and outcome, while controlling for potentially confounding variables. More specifically, multivariate logistic regression analyses will be carried out. A stepwise selection procedure will be used including all risk factors found to be statistically significant at the bivariate level in addition to those considered as being clinically meaningful. Similarly, results will be presented as OR and their corresponding 95% CI.

The primary analysis is an intention-to-treat analysis (ITT) of unadjusted results. ITT being defined as analysis of all participants as randomized, regardless of whether the participants respected the study protocol or not (effectiveness). Sensitivity analysis will be carried out as per-protocol analysis consisting of analyzing individuals according to the treatment that the participants took, independently of their randomization.

P-values will be considered statistically significant if ≤ 0.05 . SPSS version 25.0 will be used to carry out the data cleaning, management and analyses.

Ethical considerations

The RA will consent patients, right after the cardiologist consents for the standard DC cardioversion procedure, using lay language prior to cardioversion. The risks and benefits of DC cardioversion and double sequential external defibrillation, as well as alternatives to their use will be thoroughly described. A copy of the informed consent will be given to each participant.

Data collection will be carried out by CITI certified research assistants. Only the information in patient charts and records will be observed and recorded. This study will not in any way influence the decision-making process or actions of AUBMC staff treating the patient.

All data collected will be stored in a manner that restricts identifiers to the PI and on a need to know basis for other researchers, and in keeping with the ten-year safe and secure storage regulations. All data will be entered in an excel sheet located on a password-protected computer of the primary investigator. After completion of the analysis, all patient identifiers located on the excel document will be removed.

Time frame

The study is expected to start in winter 2018 and will extend over 7 years: one year for study implementation, 5 years for patient recruitment and one year for data analysis and manuscript write up. It is projected to end in winter 2025.

References

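### Is it a flaw that the trial is sized on a 28-point difference in conversion rates but plans a confidence interval only for the odds ratio?

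*Combined protocol and SAP*

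**What the plan says.** Section i) Sample size gives two planning rates. For control, "the investigators considered that 50% of patients with refractory AF will revert to sinus rhythm after 3 trials of DC cardioversion". For a third attempt by double sequential defibrillation, "Based on clinical experience, the investigators expect 78% to achieve" a positive outcome. The section then draws the consequence: "This will yield an expected difference of 28% in DSED between the intervention and control groups". With 80% power and an alpha of 0.05 it arrives at 50 patients per arm, 100 in total. It does not name the formula.

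Section j) Statistical analysis summarises categorical variables as "frequencies (percentage) for the continuous and categorical variables, respectively" and tests them with Pearson's chi-square. An effect measure with an interval appears twice. For the bivariate analysis, "results will be presented as odds ratios (OR) and their corresponding 95% confidence intervals (CI"). For the logistic regression, "Similarly, results will be presented as OR and their corresponding 95% CI". The primary analysis is then defined: "The primary analysis is an intention-to-treat analysis (ITT) of unadjusted results". That sentence names no effect measure. No interval for a risk difference or a risk ratio is planned anywhere.

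Section g) Outcome defines the outcome as a count of participants who revert, and the Hypothesis speaks of a higher success rate. Neither sets a margin or a minimum difference to be shown.

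**The concern.** The hypothesis, the outcome and the sample size are all expressed as proportions, while the only planned interval is on the odds scale. The outcome is common, so the odds ratio is far from the risk ratio: at the planning rates it is 3.55 against 1.56. A reader who took 3.55 to mean 3.55 times as likely to convert would badly overstate the effect.

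An odds ratio alone also does not fix the absolute gain, which depends on the control rate. The protocol says it found no similar published studies for its calculation, so the 50% is uncertain.

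Finally, the sentence that defines the primary analysis names no effect measure, which in principle leaves room to choose the scale after seeing the data. What would be at stake is whether the trial reports how many more patients convert, and how precisely it knows that.

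**Working it through.** **Inputs.** Control rate p0 = 0.50, intervention rate p1 = 0.78, alpha 0.05, power 80% and 50 per arm, all from section i; Pearson's chi-square from section j. Two-sided testing is assumed, because sidedness is not stated.

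**1. The plan's own figure.** With a mean rate of 0.64, a difference of 0.28, and z-values 1.960 and 0.842:

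- Difference in proportions, no continuity correction: n = [1.960 × √(2 × 0.64 × 0.36) + 0.842 × √(0.50 × 0.50 + 0.78 × 0.22)]² / 0.28² = 44.9, so 45 per arm.
- The same with continuity correction: (44.9/4) × [1 + √(1 + 4/(44.9 × 0.28))]² = 51.8, so 52 per arm.
- Wald test on the log odds ratio: n = (1.960 + 0.842)² × [1/(0.50 × 0.50) + 1/(0.78 × 0.22)] / (ln 3.545)² = 48.2, so 49 per arm.

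The stated 50 lies between the last two. The formula cannot be identified from the text, so the documents do not show that the absolute difference was the only design scale. The pair 50% and 78% fixes all three measures together: difference 0.78 − 0.50 = 0.28; risk ratio 0.78/0.50 = 1.56; odds ratio (0.78/0.22)/(0.50/0.50) = 3.55.

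**2. What the planned data would yield.** If the planning rates were observed, the counts would be 0.78 × 50 = 39 and 0.50 × 50 = 25.

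- Odds ratio: (39/11)/(25/25) = 3.545. SE of the log = √(1/39 + 1/11 + 1/25 + 1/25) = 0.443. The 95% CI is exp(1.266 ± 1.96 × 0.443) = 1.49 to 8.45.
- Risk ratio: 1.56. SE of the log = √(0.22/39 + 0.50/25) = 0.160. The 95% CI is 1.14 to 2.14.
- Risk difference: 0.28. Wilson limits are 0.648 to 0.872 for 39/50 and 0.366 to 0.634 for 25/50. The Newcombe limits are 0.28 − √[(0.78 − 0.648)² + (0.634 − 0.50)²] = 0.092 and 0.28 + √[(0.872 − 0.78)² + (0.50 − 0.366)²] = 0.442.

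All three come from the same four counts, which the chi-square test already requires.

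**3. Would the conclusion change?** Take every pair of arm counts from 0 to 50, weight each by its binomial probability at 0.50 and 0.78, and ask whether the Newcombe interval excludes 0 and whether the odds ratio interval excludes 1. The two answers differ with a total probability of about 0.4%. The power of the planned chi-square test at 50 per arm is 84.3% by the same enumeration. That test compares the two proportions directly and does not depend on the effect measure reported.

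**4. The dependence on the control rate.** Holding the odds ratio at 3.545, p1 = 3.545 × p0/(1 − p0 + 3.545 × p0). The difference p1 − p0 is then 0.303 at p0 = 0.30, 0.280 at 0.50, 0.192 at 0.70 and 0.134 at 0.80. Only the 50% is in the documents; the other control rates are assumed. The calculation shows a general property of odds ratios. The trial will observe its own control rate, so its reader will not have to choose between 13 and 30 points.

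**The case for a change.** The best case for a change is that a Phase III superiority trial should name the effect measure of its primary analysis, and section j does not do so in the sentence that defines it. The nearby odds ratio sentence follows one about independent variables and the two groups, so it may have been meant for covariates as much as for the treatment comparison. Percentages are planned as description only, with no interval, and the text does not say outright that outcome percentages will be shown by arm. The remedy would cost one or two sentences, and an interval of about 9 to 44 points would tell readers something that an odds ratio does not show directly.

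All of that is true of the text, and reporting the difference with its interval would be better practice. What does not stand is the claim that the trial could not say how precisely it estimated the absolute effect. The interval is a closed-form calculation from counts the analysis must produce. The worry about choosing a scale afterwards has little force, because the test is fixed, the odds ratio is the only measure the plan names, and the intervals on the two scales almost always agree. Nor is there a 28-point target to be met: the figure is a planning assumption, and the hypothesis asks only for a higher success rate.

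**Conclusion.** No change to the plan follows. The observation is correct: the planning effect is described as a difference, the only interval planned is for the odds ratio, and the primary analysis names no effect measure of its own. But the plan as written gives a valid test and a valid estimate, and its passages do not contradict each other. An odds ratio also fits the logistic regression planned later in section j. The effect on type I error, power and sample size is nil, and the effect on the superiority conclusion is a disagreement in about 0.4% of outcomes at the planning rates. This is a gap that an analyst fills sensibly when reporting, by giving counts and percentages by arm and the unadjusted intention-to-treat difference with its interval beside the odds ratio.

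This conclusion assumes a two-sided test, 50 patients analysed per arm and true rates near 50% and 78%. It also assumes that the counts by arm are reported, as the chi-square analysis makes natural.

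### The supportive adjusted odds ratio rests on a significance screen, stepwise selection and unnamed covariates; a short fixed model that always keeps the randomised arm would make it reproducible at little cost

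*Combined protocol and SAP*

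**What the plan says.** Section j) of the combined protocol and SAP ranks the analyses plainly: "The primary analysis is an intention-to-treat analysis (ITT) of unadjusted results". The adjusted model is an addition, with this purpose: "A multivariate analysis will be carried out for the association between the intervention and outcome, while controlling for potentially confounding variables". Its covariates are found as follows: "A stepwise selection procedure will be used including all risk factors found to be statistically significant at the bivariate level". Variables that the investigators judge clinically important also enter.

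The section does not name the clinically chosen variables, the direction of the stepwise procedure or its entry and removal thresholds. It does not say that the arm stays in the model. The screen refers back to the bivariate paragraph of the same section, which tests the "association between the independent variables (continuous and categorical) and the two groups (Intervention and control) of the outcome".

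Two other sections bear on the fix. Background information and Significance lists five predictors of failed cardioversion: age, first episode or not, heart failure, vascular disease, and a short interval since the last episode. Section h) collects data for the AF-CVS score, which is built for that prediction. Neither is tied to the adjusted model.

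**The concern.** Randomisation leaves no systematic confounding to search for, so a data-driven hunt for confounders is a poor basis for adjustment here. What adjustment can add comes from prognostic variables, and those can be named beforehand.

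The rule also cannot be carried out in one way only. The term for risk factors in the selection sentence points to a screen against outcome; the parenthesis in the bivariate sentence points to a screen against arm. Against arm, the screen picks up only chance imbalance. Against outcome, the covariate set varies with the sample. Two competent analysts could each follow the text and report different adjusted odds ratios. If stepwise removal were applied literally to every term, the arm itself could drop out and no adjusted odds ratio would be reported.

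**Working it through.** **1. The plan's own figure.** Section i) assumes that "the investigators considered that 50% of patients with refractory AF will revert to sinus rhythm after 3 trials of DC cardioversion" and, for DSED, that "the investigators expect 78% to achieve" success, with 80% power and alpha 0.05 (two-sided assumed). The pooled proportion is 0.64.
- n = [1.96√(2×0.64×0.36) + 0.842√(0.50×0.50 + 0.78×0.22)]² / 0.28² gives 45 per arm, or 52 with continuity correction. The stated 50 is close to the latter.
- Power at 50 per arm, uncorrected, is 84.1%.

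Nothing below changes this.

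**2. Failures per model term.** Expected failures are 50×0.50 + 50×0.22 = 25 + 11 = 36.
- Arm plus one score: 36/2 = 18.
- Arm plus two predictors: 36/3 = 12.
- Arm plus three: 36/4 = 9.
- Arm plus five: 36/6 = 6.

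**3. Noise in the screen.** For k unrelated, independent candidates screened at 0.05, the chance that at least one passes is 1 − 0.95^k: 40%, 54% and 64% for k = 10, 15 and 20. The candidate list in section h) is open-ended.

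**4. If the arm were open to removal at p > 0.10** (assumed; the plan gives no threshold). In an arm-only model, removal probability is about 1 minus power at alpha 0.10.
- 50% v 78%: 1 − Φ[(0.28 − 1.645×0.0960)/0.0918] = 9%.
- 50% v 64% (half the planned effect): 1 − 0.408 = 59%.
- No effect: about 90%.

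Simulated models with covariates gave 5–10% at the planned effect and 88–91% under the null. A smaller simulation (1,000 trials, 15 candidates) with a conditional odds ratio of 3.55, a somewhat weaker marginal effect, gave about 16%. In its null runs the arm survived in 10–11% of trials, and the 95% interval then covered the truth in only 42–49%.

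**5. Power with the arm kept.** Simulation: 3,000 trials per setting, 50 per arm, 20 covariates of which 3 are prognostic, log odds ratio per SD 0.3 (weak) or 0.6 (strong), screen at 0.05, backward removal at p > 0.10. The documents give none of these strengths or counts. Clinical variables means that the three prognostic ones are entered; the fixed list contains the same three. Power in %, weak / strong:

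| Model | Independent covariates | Correlated, half binary |
|---|---|---|
| Unadjusted | 83.1 / 84.5 | – |
| Arm screen only | 83.2 / 84.6 | 83.5 / 84.7 |
| Outcome screen only | 82.5 / 86.3 | 85.1 / 90.8 |
| Arm screen + clinical variables | 84.6 / 89.0 | – |
| Outcome screen + clinical variables | 83.8 / 88.0 | – |
| Fixed three-variable list | 85.1 / 89.2 | 86.0 / 90.6 |
| One score, correlation 0.5 with true risk | 83.6 / 85.7 | 84.1 / 85.7 |

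The plan does enter clinical variables, so the relevant gains for independent covariates are 85.1 − 84.6 = 0.5 and 85.1 − 83.8 = 1.3 (weak), and 89.2 − 89.0 = 0.2 and 89.2 − 88.0 = 1.2 (strong). A repeat with 1,500 trials per setting, covering correlated covariates too, gave 0.1 to 1.6. The single score differs from the outcome screen alone by +1.1 / −0.6 points (independent) and −1.0 / −5.1 (correlated).

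**6. Spread between readings.** With clinical variables entered, the arm and outcome readings give odds ratios at least 10% apart in 26% / 28% of trials (32% / 40% correlated), but different significance calls in only 2–3%.

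**7. Validity with the arm kept.** Coverage of the conditional odds ratio is 93.8–95.1% under the outcome screen and 94.4–95.7% for the fixed three-variable list. Null rejection is 4.9–6.3% for selected models and 5.2–5.6% for fixed lists (simulation SE 0.4). The repeat with clinical variables entered gave 6.4–6.5% against 5.5% (SE about 0.6).

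**8. Scale of the adjusted odds ratio.** The marginal value is (0.78/0.22)/(0.50/0.50) = 3.55. The implied conditional value is 3.81 / 4.60 (independent) or 3.89 / 4.90 (correlated), so a difference between the two is expected and is not an error.

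**The case against.** The strongest reply is that little is at stake. The primary analysis is fixed as unadjusted. The clause on clinically chosen covariates means that a screen-only model is not the planned model. The stated purpose of the model disfavours any reading in which the arm is removed, and one clause on retention would settle that. A single score could even have less power than the outcome screen. All of this stands, and it limits the size of the point.

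It also rules out four stronger inferences that a reader might draw:
- **The trial's main conclusion or its error rate is at risk.** The adjusted model is not primary.
- **The arm will be dropped.** The text only omits to say that it is kept; the percentages in step 4 depend on a literal reading and an assumed threshold.
- **Screening against arm forfeits the precision gain.** That happens only if the clinical variables are absent or badly chosen, and a fixed list depends on equally good choice.
- **The intervals are invalid because they ignore selection.** Coverage with the arm kept shows no material harm.

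A retention clause alone is not enough, however. It secures the arm but leaves the covariates to the sample and the analyst, and the target of the screen unresolved.

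**Conclusion.** The point holds as a modest one about method and reproducibility. The plan specifies a data-driven selection for a randomised comparison, with an unclear screening target, unnamed clinical covariates and no statement that the arm is retained. A better method is available from predictors that the document already lists.

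Only the supportive adjusted odds ratio is affected. The power gain from a fixed list is about 0 to 1.5 points once sensible clinical variables are entered, so power is not the reason to change. The reason is one pre-specified adjusted odds ratio that any analyst would reproduce and that is always reported. The sizes rest on assumed prognostic strengths, candidate numbers and a removal threshold that the documents do not give. The gaps in the text do not depend on those assumptions.

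**What to change.** In section j), delete the significance screen and the stepwise step. Before outcome data are seen, name one supportive logistic model: the randomised arm, stated as always retained, plus two or three baseline predictors of failed cardioversion that the data collection form records, for example from the five in Background information and Significance. The AF-CVS score as a single term is only an alternative: its cited source concerns acute AF, section c) enrols persistent AF, and a weak score can lose power.

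State that the adjusted odds ratio is conditional and is expected to differ from the unadjusted one. Reword the bivariate sentence so that it is clear whether variables are tested against arm or outcome. Keep unadjusted intention-to-treat as primary.

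The cost is a few sentences, with no change to the sample size and no new data if Appendix 1 (not supplied) collects the chosen predictors. The downsides are no freedom to add covariates later, little gain if the predictors prove weak, and a small-sample overstatement of the conditional odds ratio of about 5–10% with three covariates in the simulation (8–14% with five, which favours the shorter list).

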Cover Page

Double sequence external defibrillation:
A randomized controlled trial in
patients with atrial fibrillation
refractory to DC cardioversion

Date: 31/1/2019

NCT ID not yet assigned

Background information and Significance

Atrial fibrillation (AF) is the most common sustained cardiac arrhythmia in clinical practice. Patients are at increased risk for death, heart failure, hospitalization, and thromboembolic events [1-3]. In one study by Go et al., it was shown that the overall prevalence of AF was 1%; ranging from 0.1% among adults less than 55 years of age to 9% in those ≥ 80 years of age [4]. The restoration (cardioversion) of sinus rhythm is performed in many patients with AF to improve symptoms. Therefore, some physicians attempt to restore sinus rhythm ('rhythm control' strategy) in patients with AF, either using drugs ('pharmacological cardioversion') or by direct current (DC) shocks ('electrical cardioversion'). Electrical cardioversion requires admission to the hospital, a short-acting anesthetic and a direct current shock. Sometimes repeated cardioversions are required if a patient spontaneously reverts to AF. There are two important reasons why cardioversion might be useful. Firstly, successful restoration of sinus rhythm may reduce the risk of embolic complications, thereby obviating the need for long term anticoagulation, with its attendant risks [5]. Secondly, observational studies have shown that after successful restoration of sinus rhythm, left ventricular function improves [6], atrial and ventricular function normalizes [7], and that after restoration of atrial contractility, left ventricular ejection fraction and maximal exercise capacity both improve [8]. Electrical cardioversion (ECV) is the standard treatment for acute AF, but identification of patients with increased risk of ECV failure or early AF recurrence is of importance for rational clinical decision-making. A study by Jaakkola et al. showed that the risk of unsuccessful outcome of Electrical Cardioversion (ECV) can be predicted using 5 simple clinical variables: age, whether or not it is the first AF, cardiac failure, vascular disease and whether or not there's a short interval from the previous AF episode [9]. In obese patients for instance, high impedance can also decrease the effective energy delivered to the atria in large-bodied patients [10]. AF has been treated with DC shocks delivered trans-thoracically, but in 5-30% of patients, the procedures fail to restore sinus rhythm (SR) [11]. Higher energy external DC cardioversion (DCC) has long been used for ventricular arrhythmias [12, 13]. There have been some studies that have reported on the delivery synchronized higher energy external DCC as an alternative approach for cardioversion in patients with AF refractory to conversion with standard external cardioversion energies [14, 15].

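### Optional gain: make one prespecified AF-CVS score a covariate in the primary ITT test; the unadjusted test is valid and adequately powered, but leaves collected prognostic data unused

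*Combined protocol and SAP*

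**What the plan says.** Section j (Statistical analysis) names the confirmatory comparison: "The primary analysis is an intention-to-treat analysis (ITT) of unadjusted results". It names Pearson's chi-square for categorical variables. It also plans a multivariate logistic regression of outcome on intervention. The covariates there come from a stepwise procedure fed by bivariate significance and clinical judgement, and that model is not primary.

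The Background says that the risk of failed electrical cardioversion "can be predicted using 5 simple clinical variables": age, first AF episode or not, cardiac failure, vascular disease, and a short interval since the previous episode. Section h (Other factors and data collection) adds: "Data will be related to AF and to the risk stratification tool (AFCVS score").

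Section i (Sample size) works from two raw proportions. For control it assumes that "50% of patients with refractory AF will revert to sinus rhythm after 3 trials of DC cardioversion". For DSED it takes 78%, on clinical experience. It then concludes: "Considering a power of 80% and an alpha of 0.05", "the investigators will require 50 patients in each arm, a total of 100 patients". Section e (Randomization) uses permuted blocks of 4, 6 and 8 and names no stratification factor.

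**The concern.** The plan identifies a prognostic score, intends to record it, and then leaves it out of the one confirmatory comparison. Because randomisation is not stratified, nothing in the design balances the score either. With 100 patients, outcome variation that a baseline score could explain is treated as noise, and a chance difference in prognosis between arms passes straight into the primary result. The planned adjusted model cannot do this job, because its covariates are chosen from the data. At stake are a few points of power, and some protection for the one trial that will be run, under an effect assumption that rests on clinical experience.

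**Working it through.** **Inputs from section i:** control 0.50, DSED 0.78, difference 0.28, alpha 0.05, power 80%, 50 per arm. Sidedness is not stated; two-sided is assumed.

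**1. The plan's sample size.** The mean proportion is (0.50 + 0.78)/2 = 0.64.

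- n per arm = [1.960·√(2·0.64·0.36) + 0.8416·√(0.50·0.50 + 0.78·0.22)]² / 0.28²
- = [(1.3305 + 0.5465)/0.28]² ≈ 44.9, so 45 per arm.

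With continuity correction the answer is 52, and by Fisher's exact test 51. The plan's 50 is close to these two variants.

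**2. Power of the planned unadjusted test at 50 per arm.**

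- z = [√50·0.28 − 1.3305]/√0.4216 = (1.9799 − 1.3305)/0.6493 = 1.000
- Power = 84.1% (84.3% by exact enumeration).

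With Yates' correction or Fisher's test it is 78.9%. The plan names Pearson's chi-square, so the 80% target is met.

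**3. Gain from one prespecified score, by formula.** Prognostic strength is not in the documents, so a range is assumed. If the score explains a share R² of outcome variance, the effective size is 50/(1 − R²) per arm. For R² = 0.10 this is 55.6, z = (√55.6·0.28 − 1.3305)/0.6493 = 1.165, and power is 87.8%.

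| Assumed R² | 0 | 0.02 | 0.05 | 0.10 | 0.15 |
|---|---|---|---|---|---|
| Power | 84.1% | 84.9% | 86.0% | 87.8% | 89.6% |

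**4. The same by simulation.** There were 10,000 trials per setting, 50 per arm, with one standard-normal score and marginal success of 50% and 78%. Chi-square was compared with the logistic likelihood-ratio test of arm adjusted for the score.

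| Score OR per SD (approx. R²) | Unadjusted | Adjusted |
|---|---|---|
| 1.0 (0) | 84.6% | 84.9% |
| 1.65 (0.05) | 84.2% | 86.2% |
| 2.1 (0.10) | 84.3% | 88.2% |
| 2.7 (0.16) | 84.4% | 90.1% |

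Weaker scores, in 5,000 trials each, gave 84.2% v 84.8% at a c-statistic of 0.56 and 84.8% v 85.8% at 0.58. If the score predicts only in the control arm (c 0.70), the result is 85.2% v 86.2%.

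**5. Type I error** with 64% success in both arms was 5.0% to 5.4% for the one-score model, against 4.6% to 5.3% for chi-square. Shorter runs for one score ranged from 4.4% to 5.8%. Entering five separate covariates gave 5.3% to 6.1%. Only 50·0.50 + 50·0.22 = 36 failures are expected, or 6 per parameter for arm plus five covariates, so one score is the safer form.

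**6. Chance imbalance.** The between-arm difference in mean score has SD √(2/50) = 0.2, so a gap of at least 0.3 SD (z = 1.5) arises in about 13% of trials. Under the null, the unadjusted test rejected in 7% to 10% of those trials and the adjusted test in 4% to 6%. When such a gap disfavours DSED (about 7% of trials), power was 68%, 64% and 57% unadjusted against 82%, 86% and 92% adjusted, for score coefficients of 0.5, 0.8 and 1.1 per SD.

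**7. Missing scores.** With 10% missing (an assumption) and coefficient 0.5, complete-case adjustment loses power: 83.9% unadjusted v 82.6% adjusted. Replacing missing scores with the overall mean restores the gain: 84.4% v 86.4%.

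**The case against.** The case for leaving the plan alone is substantial.

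- **Nothing is broken.** Unadjusted ITT is valid, leaves no discretion over covariates, and matches the proportions used for sizing. This stands in full.
- **The score may be weak here.** The reference cited for AF-CVS concerns acute AF. Section c enrols persistent AF after two failed attempts, so patients are selected on the very event that the score predicts. The gain may be near zero. This stands.
- **An adjusted analysis is already planned.** True, and it may include covariates judged clinically meaningful. But it is not primary and its covariates are selected stepwise, so it does not supply prespecified adjusted inference.
- **Adjustment has costs.** The adjusted OR is a conditional effect, not the marginal difference used for sizing, and complete-case handling could turn the gain into a loss while departing from the plan's own ITT definition. Both can be managed, but both must be written down.

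A reader might go further and infer that the trial discards power it could have free of charge, or that it falls short without adjustment. The documents do not support this: the named test exceeds 80%, the size of any gain is unknown, and the costs are small but real. A reader might also infer that all five predictors are certainly recorded for every patient. Section h says that the data will relate to AF-CVS, but its list does not name first episode or interval since the previous episode. Appendix 1, which is not in the text available, may well include them.

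**Conclusion.** This is an inexpensive improvement and optional. The primary analysis as written is valid, with about 84% power under the plan's own assumptions. One prespecified AF-CVS score in the primary model would add about 0 to 6 points, for an assumed R² between 0 and about 0.16, with essentially no loss at R² = 0 and type I error close to 5%. It would also limit the effect of a chance imbalance. These figures assume two-sided 5% testing, a roughly normal score that acts linearly on the logit with the same strength in both arms, and no patients lost for want of a score. The case rests less on the size of the gain, which may be close to nil here, than on the small price of trying for it.

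**What to change.** Amend section j, before outcomes are examined by arm, as follows.

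- **Primary analysis:** ITT logistic regression of conversion to sinus rhythm on randomised arm plus AF-CVS score as a single linear term, using values recorded before randomisation.
- **Missing scores:** replace with the overall mean pooled across arms, so that every randomised patient stays in. Do not use complete cases.
- **Reporting:** the likelihood-ratio p-value and the adjusted OR with 95% CI, beside the unadjusted OR and risk difference. State that the adjusted OR is conditional and that the sample size came from unadjusted proportions.
- **Supportive:** the unadjusted Pearson chi-square.
- **Data capture:** confirm that Appendix 1 records all five items before the envelope is opened. Section h places the interview only after consent.

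The cost is SAP wording and a check of the form. If the items are not now captured before allocation, a small procedural change is also needed. No extra patients are required, and the planned software can fit the model.
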